### Power analysis

Given the previous natural history data, which indicates that only 1 out of 29 individuals experienced subtle changes in the paramagnetic rim over the long term (a period of several years), we would expect that very few to no untreated participants will experience changes in the short time period observed in this study. Thus, even 1 participant experiencing short term changes would potentially be clinically meaningful. Using an estimated null proportion of individuals with lesion changes of 0.01, a cohort of 5 participants achieves 80% power to detect a difference of 0.27 using a one-sided binomial exact test with a significance level of 0.05. The null hypothesis will be rejected if 1 individual experiences at least one lesion change.

Participants who drop out or in whom anakinra is stopped will be replaced, up to the accrual ceiling or until there are 5 completers — whichever comes first.

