## 3. Subjects

### Description of study populations

This protocol will enroll up to 10 individuals with progressive or stable MS, evidence of chronic active lesions in the white matter (by MRI), and no evidence of new lesion formation in the prior 3 months or clinical relapse in the prior 12 months (by analysis of prior off-protocol MRI scans). We aim to achieve 5 study completers. NIH employees, regardless of their status as subordinates, relatives, or coworkers of investigators, are eligible.

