## 10. Statistical Analysis

### Analysis of data/study outcomes

The primary outcome is the per-patient proportion of lesions in which the paramagnetic rim has been modulated at the end of the dosing period. Proportion of diminished/resolved paramagnetic rims will be analyzed by investigators blinded to time point, reported descriptively, and compared to the assumption of no change off therapy (11, 16) — a reasonable assumption since we have never observed complete disappearance of a chronic rim — via Binomial exact tests.

For the secondary outcome measures, safety and tolerability will be assessed qualitatively; AEs will be tabulated and compared to prior published and unpublished (to the extent possible) data on anakinra. Quantification will include the proportion of participants who start anakinra therapy and complete the full dosing. MRI outcomes will be reduced to scalar measures at various time points. Longitudinal changes in rim presence/absence, T1 relaxation time, and lesion volume will be analyzed by analysis of variance or mixed-effects models (which naturally handle missing data), the latter two in comparison to

CNS IRB Protocol Template (5.4.17)

non-rim lesions. Analyses will be performed both in completers and on an intent-to-treat basis. There will be no interim analysis.

Analysis methods for exploratory outcome measures will be determined by the study team and collaborators at a later time point.

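### The one-event rejection rule keeps its 0.05 level only when 5 or fewer participants are analysed, but the plan allows up to 10 enrolled and does not say which set carries the primary test

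*Combined protocol and SAP*

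**What the plan says.** The relevant statements are in Sections 3 and 10 of the protocol.

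- **Design inputs (Section 10, Power analysis).** The calculation is made "Using an estimated null proportion of individuals with lesion changes of 0.01", and finds that "a cohort of 5 participants achieves 80% power to detect a difference of 0.27". The test named for this is exact binomial, one-sided, at 0.05.
- **Decision rule (same paragraph).** "The null hypothesis will be rejected if 1 individual experiences at least one lesion change". No version is given for any other number of participants.
- **Replacement (next paragraph).** "Participants who drop out or in whom anakinra is stopped will be replaced, up to the accrual ceiling or until there are 5 completers".
- **Ceiling (Section 3, Description of study populations).** "This protocol will enroll up to 10 individuals with progressive or stable MS", with the aim of reaching 5 completers.
- **Analysis sets (Section 10, Analysis of data/study outcomes).** "Analyses will be performed both in completers and on an intent-to-treat basis". Neither set is defined, and the text does not say which one carries the primary binomial test.

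**The concern.** The rule is a count with no denominator. It is calibrated for 5 people, and replacement can raise the number treated above 5. Under an intent-to-treat analysis, replaced participants stay in, so one replacement after dosing makes the set at least 6.

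With a null this small and a threshold of one event, the whole inference rests on a single participant. If exactly one person changes and six are analysed, the written rule rejects while the named exact test does not. The plan gives no way to decide between them, so the choice would be made after the result is known.

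**Working it through.** **Inputs.** From Section 10: null proportion 0.01; difference 0.27, so the alternative is 0.01 + 0.27 = 0.28; n = 5; one-sided exact binomial test at 0.05; reject on 1 or more individuals. From Section 3: at most 10 enrolled.

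**Step 1: reproduce the plan's figure.**
- Level at n = 5: 1 − 0.99^5 = 1 − 0.9510 = 0.0490.
- Power at n = 5: 1 − 0.72^5 = 1 − 0.1935 = 0.8065.

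Both agree with the stated 0.05 and 80%.

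**Step 2: slack in the rule.** The largest null proportion that keeps the one-event rule at 0.05 is 1 − 0.95^(1/n). This is 0.0102 at n = 5, 0.0085 at n = 6 and 0.0051 at n = 10. The assumed 0.01 fits at n = 5 with almost nothing to spare.

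**Step 3: other values of n.** With every analysed person able to show an event:
- P(at least 1) = 1 − (1 − p)^n
- P(at least 2) = 1 − (1 − p)^n − n·p·(1 − p)^(n−1)

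The level uses p = 0.01 and the power uses p = 0.28.

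| n | Level, 1 event | Level, 2 events | Power at 0.28, 1 event | Power at 0.28, 2 events |
|---|---|---|---|---|
| 4 | 0.0394 | 0.0006 | 0.731 | 0.313 |
| 5 | 0.0490 | 0.0010 | 0.807 | 0.430 |
| 6 | 0.0585 | 0.0015 | 0.861 | 0.536 |
| 7 | 0.0679 | 0.0020 | 0.900 | 0.627 |
| 8 | 0.0773 | 0.0027 | 0.928 | 0.703 |
| 9 | 0.0865 | 0.0034 | 0.948 | 0.766 |
| 10 | 0.0956 | 0.0043 | 0.963 | 0.817 |

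The one-event level is also the exact one-sided p-value for a single event. From n = 6 to n = 10 that p-value exceeds 0.05, so an exact 0.05-level test needs 2 events.

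**Step 4: who can contribute an event.** The chance that the one-event rule rejects under the null depends on how many people can show a change, not on how many are listed. If m of the n can be assessed and the rest count as unchanged, it is 1 − 0.99^m. With m = 5 it is 0.0490 at any enrolment.

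**Step 5: sensitivity to the null.**
- At 0.005, the one-event rule gives 0.0248 at n = 5 and 0.0489 at n = 10, so it holds throughout.
- At 1/29 = 0.0345, the proportion behind the plan's natural-history argument (observed over several years, so an upper comparison here), it gives 0.161 at n = 5 and 0.296 at n = 10.

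**The case against.** The strongest reply is that the rule was never meant to leave n = 5. It directly follows the calculation for that cohort, replacement exists to deliver 5 completers, and the Study overview in Section 4 ties full analysis to all 5 having finished. On 5 completers the level is 0.0490. The intent-to-treat sentence also closes a paragraph that opens on secondary outcomes, so it may not govern the primary test. **What stands:** this is a fair reading, and the stated arithmetic is correct. But the sentence is worded without restriction and is followed by a study-wide statement on interim analysis. No text assigns the binomial test to completers.

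A second reply is that replaced participants may add little chance of an event. The primary outcome is read when dosing ends, and Section 8 gives those who choose to withdraw one final visit limited to safety. **What stands:** the larger levels need replaced people who were dosed and could be assessed. Someone replaced before dosing because the lumbar puncture was not tolerated need not add to a dosed set. However, Section 8 keeps participants who stop for dose-limiting toxicity in follow-up, with visits that include MRI, so some replaced people can be assessed.

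A third reply is that moving from 4.9% to 5.9% is small in an uncontrolled pilot whose null is itself an estimate. **What stands:** the excess after one replacement is smaller than the uncertainty in the null. The disagreement between rule and test on a single event remains.

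A reader might also infer that replacements are likely. The documents give no dropout rate, and the background describes anakinra as well tolerated in earlier rheumatoid arthritis trials, so that inference is unsupported.

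**Conclusion.** The point holds in a conditional form. At the plan's own null of 0.01, the one-event rule has its stated level only for 5 or fewer analysed. Applied to an intent-to-treat set with replaced participants who were dosed and assessable, its level is 0.0585 at n = 6 and at most 0.0956 at n = 10. The upper figure needs 10 enrolled, all dosed and all assessable.

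A reader might conclude that the sample size calculation is wrong, or that the trial's false-positive rate is 9.6%. The documents support neither. The calculation reproduces, and the level stays at 0.0490 with exactly 5 completers or if non-completers count as unchanged. What is missing is a statement of which convention applies.

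The completer set is not yet a complete answer either. Under Sections 4 and 9, a participant whose baseline rims have all disappeared leaves treatment early. The replacement wording in Section 10 covers anyone whose anakinra is stopped and makes no exception for this reason. Completers are not defined, so it is unclear whether such a responder would count in that set.

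**What to change.** Amend Section 10 as follows.

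1. Name the set that carries the primary binomial test. One option is the 5 completers, with the intent-to-treat result reported alongside as supportive with its own exact p-value. Making all dosed participants primary is also possible, but nothing in the documents requires it.
2. State how non-completers count in that set, and how participants whose treatment ends early for efficacy count, including whether the replacement rule applies to them.
3. Limit the one-event rule to an analysed n of 5 or fewer. For any other n, base the conclusion on the one-sided exact binomial p-value at the n analysed, which at a null of 0.01 means 2 events for n = 6 to 10. Alternatively, keep one event for every set and restate its level as up to 9.6%.

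The cost is a few sentences if completers are primary, with no loss of power. If the intent-to-treat set is primary, the cost should be disclosed: the two-event threshold gives power at 0.28 of about 0.54 at n = 6, rising to 0.82 at n = 10, against 0.81 for the planned design. Its level is then only 0.0015 to 0.0043, because no threshold between one and two events exists.

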## Précis:

- *Objective.* The overall goal of this study is to determine the safety, tolerability, and radiological efficacy of up to 12 weeks of subcutaneous injection of anakinra in people with multiple sclerosis and evidence, by magnetic resonance imaging (MRI), of chronic active (also known as “smoldering”) lesions in the white matter.
- *Study population.* 5 people with progressive or stable MS, at least one paramagnetic rim lesion on 7-tesla MRI, and no new white matter lesion formation for at least 3 months or clinical relapse for at least 12 months, will complete the study.
- *Design.* In this open label, dose escalation study, participants will receive up to 12 weeks of subcutaneous anakinra with initial dose of 100 mg daily up to a target dose of 300 mg daily. Study visits will occur every 4 weeks while on treatment, with 2 follow-up visits at 4 and 12 weeks after treatment discontinuation.
- *Outcome measures.* The primary outcome measure is disappearance of one or more paramagnetic rims from white matter lesions identified at baseline. Secondary outcomes include safety and tolerability, clinical and radiological outcomes. Exploratory serological and CSF measures will also be obtained to investigate mechanism of action of anakinra and for biomarker development.

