## Inclusion criteria

### ***Inclusion criteria:***

- Age  $\geq 18$
- Ability to give informed consent
- If fertile, agreement to use an effective method of birth control during the study and for up to 3 months after the last dose of the study drug
- Agreement not to participate in any other interventional study while participating in this protocol
- Diagnosis of MS, either stable or clinically progressive
- Prior 7-tesla MRI scan, with high image quality in the judgment of the study neuroradiologist, demonstrating at least one white matter lesion with a paramagnetic rim (41)

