## 4. Study Design and Methods

### Study overview

Screening will be done under an existing Neuroimmunology Clinic protocol that allows collection of data required for determining eligibility. Prospective participants who meet eligibility requirements will then provide informed consent and undergo baseline procedures. Following training on self-administration of subcutaneous injections, subjects will be started on initial dose of study drug of 100 mg/d. Participants will have a scheduled follow-up phone call at 24–48 hours following the first dose to assess for any adverse reactions or concerns. Subsequent routine assessment of tolerability and safety will be made at the time of scheduled study visits. For the duration of the study, including dose escalation and follow-up phases, participants will undergo assessments at NIH. Telehealth may be used for conducting routine visits to the NIH Clinical Center. Participants will return at weeks 4 and 8, at which time they will undergo clinic visit, lab work, and 7T brain MRI. As long as no treatment-limiting toxicity is encountered (see “safety endpoints,” Section 8.4) AND the study endpoint is not met (see “efficacy study endpoint,” primary outcome, section 9), the dose will be escalated every 4 weeks to a target dose of 300 mg/day, which will be administered for a further 4 weeks. The final on-treatment study visit will be at week 12. At that time, the drug will be discontinued, with off-treatment visits at weeks 16 and 24 (4 and 12 weeks following treatment discontinuation). The study timeline is in **Error! Reference source not found..**

## Fig. 2

- **MRI at week 24 will be done without Gadolinium, unless clinically indicated.**

Should early drug discontinuation occur, either due to dose-limiting toxicity or to achievement of efficacy endpoint, off-treatment follow-up visits will proceed 4 and 12 weeks after treatment interruption. If a 7T scan cannot be obtained within window at any particular study visit, a 3T MRI can substitute. Leftover biological samples will be stored for future analysis.

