## Criteria for Early Discontinuation of Dose Escalation

Dose escalation will be discontinued in the following situations:

- Dose Limiting Toxicity is observed, as defined in Section 8.
- Efficacy Study Endpoint is achieved, as defined in Section 9.

CNS IRB Protocol Template (5.4.17)

- The patient is found to be pregnant.
- The patient, for any reason, is unwilling to continue treatment with study drug.

In the event of early discontinuation of dose escalation, the patient will proceed directly to the off-treatment follow-up phase of this study.

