- *Imaging safety criteria.* Appearance of new contrast-enhancing lesions or obvious enlargement of existing lesions on any single scan, in the opinion of the study neuroradiologist, will constitute reason for withdrawal of individual patients from the study. While new contrast enhancement could simply be due to the relapsing-remitting nature of this disease, it could also indicate unintended and unexpected exacerbation of CNS inflammation resulting directly or indirectly from modulation of the immune network by the study drug.

The reasons for discontinuation of the study drug will be recorded in the participant's Clinical Center patient file. These subjects will remain in the study and complete follow-up study visits (4 and 12 weeks following dosing discontinuation).

If discontinuation was because of an AE, the participant will be followed until the event is resolved or stabilized. If the discontinuation was because of pregnancy, the participant will be followed until after delivery.

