## 9. Outcome Measures

### Primary outcome measures

The primary outcome measure is the presence or absence of a paramagnetic rim around chronic active white matter MS lesions, assessed at the end of the dosing period.

Definition of efficacy endpoint: disappearance of one or all paramagnetic phase rims. At each study visit, paramagnetic phase rims will be assessed. For the purposes of dose escalation, if at any on-treatment scan, all paramagnetic rims that were present at baseline are no longer seen, dose escalation will end and the subject will proceed into the post-treatment follow-up phase of the study.

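### The replacement rule has no exception for participants whose drug stops because all rims have gone, and *completer* is undefined, so the stated power and one-event rule hold on only one reading

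*Combined protocol and SAP*

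**What the plan says.** **Replacement.** Section 10, Power analysis: "Participants who drop out or in whom anakinra is stopped will be replaced, up to the accrual ceiling or until there are 5 completers". No reason for stopping is excepted. The accrual ceiling is 10 (section 3, Description of study populations).

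**Efficacy is a reason for stopping drug.** Section 4, Study overview, names two causes together: "Should early drug discontinuation occur, either due to dose-limiting toxicity or to achievement of efficacy endpoint". In section 4, Criteria for Early Discontinuation of Dose Escalation, reaching the efficacy endpoint is one of the listed reasons, after which "the patient will proceed directly to the off-treatment follow-up phase of this study". Section 9, Primary outcome measures, gives the trigger: "if at any on-treatment scan, all paramagnetic rims that were present at baseline are no longer seen, dose escalation will end". Scans at weeks 4 and 8 make an early stop possible.

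**Completer.** The term is not defined, and the nearby wording points in different directions:
- The Précis says that 5 people with no recent new lesion or "clinical relapse for at least 12 months, will complete the study", and section 3 says "We aim to achieve 5 study completers". Section 4, Study overview, speaks of 5 participants having been through every study procedure. All three concern finishing the study.
- Section 10, Analysis of data/study outcomes, uses a separate phrase, about finishing the whole course of dosing, for a tolerability measure.
- Section 8, Criteria for individual subject withdrawal, treats most dose-limiting toxicities as grounds for withdrawing the participant from the study. The same section then says of participants who stop study drug: "These subjects will remain in the study and complete follow-up study visits (4 and 12 weeks following dosing discontinuation".

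**Analysis sets.** Section 10 asks for analyses in completers and by intent to treat. It does not say which carries the primary test.

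**The concern.** The design rejects its null hypothesis on one responder among 5, so the classification of one person can settle the primary result. The replacement rule, as worded, reaches the clearest kind of responder: someone who has lost every rim by week 4 or 8. Entry requires a scan "demonstrating at least one white matter lesion with a paramagnetic rim", so for a participant with a single rim any disappearance is complete disappearance.

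If the replaced person is also not counted as a completer, the completer set is selected on the outcome it is meant to measure. If the person is counted by intent to treat and a replacement is added, more than 5 are analysed, and the one-event rule no longer has the level stated for it. The study is open label, so leaving the term undefined means the reading could be chosen after the responders are known.

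**Working it through.** **Inputs, all from the Power analysis section unless noted.** Null proportion p0 = 0.01; difference 0.27, so the alternative is 0.01 + 0.27 = 0.28; n = 5; one-sided exact binomial test at 0.05; reject if at least one participant shows a change. Participants are counted, as that section does. The early stop is taken as loss of all baseline rims, the trigger section 9 gives for dose escalation (the same section also defines the efficacy endpoint as loss of one or all rims).

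**Step 1. The plan's own figure.** Chance of at least one event in n = 1 − (1 − p)^n.
- Alpha: 1 − 0.99^5 = 0.0490.
- Power: 1 − 0.72^5 = 0.8065.

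The stated 80% is correct for 5 participants.

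**Step 2. One early complete responder, no other responder, no other drug stop.**

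| How the participant is handled | Result | Exact one-sided p | 95% Clopper-Pearson |
|---|---|---|---|
| Replaced and not a completer | 0/5 | 1 | 0 to 52% |
| Replaced, all counted by intent to treat | 1/6 | 1 − 0.99^6 = 0.0585 | 0.4 to 64% |
| Counted as a completer, not replaced | 1/5 | 1 − 0.99^5 = 0.0490 | 0.5 to 72% |

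The first row does not reject and the third does. The second rejects under the one-event rule as written, but not by the exact p-value at 0.05.

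**Step 3. Level of the one-event rule by number analysed, 1 − 0.99^n.**

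| n | 5 | 6 | 7 | 8 | 9 | 10 |
|---|---|---|---|---|---|---|
| Alpha | 0.0490 | 0.0585 | 0.0679 | 0.0773 | 0.0865 | 0.0956 |

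The rule exceeds 0.05 as soon as a sixth participant is counted, whatever the reason for the replacement. Requiring 2 responders gives 0.0015 at n = 6 and 0.0043 at n = 10.

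**Step 4. Where the effect stops.** Add one partial responder who stays on drug: the sets become 1/5 (p = 0.049), 2/6 (p = 0.0015) and 2/5 (p = 0.001), and all reject. A participant who loses some but not all rims, or who first clears all rims at week 12, has no early efficacy stop.

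**Step 5. Dependence on p0.** One event rejects when p0 is at most 1 − 0.95^(1/n): 0.0102 at n = 5 and 0.0085 at n = 6. So 0/5 against 1/5 differs for any p0 up to 0.0102, while 1/5 against 1/6 differs by exact p-value only between 0.0085 and 0.0102, which contains the plan's 0.01. At the long-term figure of 1/29, 1/5 gives p = 0.16 and 1/6 gives p = 0.19; neither rejects.

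**Step 6. Power on the exclusionary reading (illustration).** Let f be the share of responders who clear all rims by week 4 or 8. The documents do not give f, so a range is assumed. The chance that a completer is not a responder is 0.72/(1 − 0.28f), and completer power is 1 − [0.72/(1 − 0.28f)]^5.

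| Assumed f | Completer power | Loss from 0.807 |
|---|---|---|
| 10% | 0.777 | 0.030 |
| 25% | 0.722 | 0.085 |
| 50% | 0.589 | 0.218 |

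The last column is the chance that this reading turns a rejection into a non-rejection, provided the completer set governs.

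**The case against.** A reader might infer that the plan throws out its best responder. The documents do not go that far.

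- The Power analysis section says such a person is replaced. It never says that a replaced person leaves an analysis.
- The Précis, section 3 and the Study overview speak of completing the study. Section 8 calls toxicity stops withdrawals from the study, a label never given to efficacy stops, which move into a planned next phase.
- Section 10 uses different words for finishing the dosing, which suggests that *completer* means something else.
- The primary outcome is assessed when dosing ends, and for an efficacy stop that is the scan that triggered it.
- The intent-to-treat set keeps the person, and a secondary outcome in section 9 counts rims diminished or gone at any visit, so the response would be visible in any report.

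A reader might also infer that intent to treat fails to reject at 1/6. Under the one-event rule as written, it rejects; the fault there is the level, 0.0585.

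These points stand, and they make the benign reading the more natural one. They do not settle it. Section 8 also keeps participants who stop drug in the study through both follow-up visits, so finishing follow-up cannot by itself separate an efficacy stop from a toxicity stop. The replacement sentence covers both without distinction. The setting is also narrow: the plan reports never having seen a chronic rim disappear completely, and this is a five-person pilot.

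**Conclusion.** The point holds as a gap in the replacement rule and the analysis-set definitions. Followed as written, the plan replaces an early complete responder. Exclusion from the completer set is one reading of an undefined term, not something the plan states. The power figure is right: alpha 0.049 and power 80.7% at 0.28, on condition that efficacy stops count among the 5.

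On the exclusionary reading the completer result moves from 1/5 to 0/5. In the intent-to-treat set, the one-event rule runs at 0.0585 for 6 participants and up to 0.0956 for 10, against a stated 0.05. The conclusion changes only where no responder is left after setting aside those who clear all rims by week 4 or 8; the simplest case is a single such responder. The figures rest on p0 = 0.01 and on counting participants; those involving f rest on an assumed range. It should be fixed before analysis.

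**What to change.** 1. Reconcile section 4 (Study overview; Criteria for Early Discontinuation of Dose Escalation), section 8 (Criteria for individual subject withdrawal), section 9 (Primary outcome measures) and section 10 (Power analysis). State, for replacement and analysis only, that a participant whose drug stops because the efficacy endpoint is met counts as a completer and is not replaced. Define *completer* so that toxicity stops are not included.
2. State that the one-event rule keeps its 0.05 level only when 5 or fewer are analysed, and that 2 responders are needed for 6 to 10. Report the exact p-value and Clopper-Pearson interval at the actual n for both the completer and intent-to-treat sets.
3. State before analysis which set carries the primary test, noting that the published power and one-event rule apply to the 5-participant set. The choice is the sponsor's: a completer set would still drop a responder who stops for toxicity, while an intent-to-treat set above 5 needs 2 responders (power 54% at n = 6 and 82% at n = 10, if 0.28 applies to everyone who starts).

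**Cost.** Wording, plus one fewer replacement when an efficacy stop occurs. No dosing or stopping rule changes. With 5 completers, alpha stays at 4.9% and power at 80.7%. If the ceiling leaves 4 or 3, the one-event rule still holds its level (3.9%, 3.0%), with power 73% or 63%. The downside is that, if someone else is replaced, the intent-to-treat analysis may not reject when the completer analysis does (1/6 against 1/5).
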